## Layperson summary

This study is part of a larger multipart study. In the current phase, we will examine the effects of social engagement during in-home exercise on a small sample of individuals with Parkinson Disease (PD). This pilot investigation will directly measure the effect of social support and engagement on exercise outcomes for rural dwelling individuals with PD.

## **Project Summary**

The benefits of exercise for individuals with Parkinson disease (PD) have been well documented; however, individuals with PD living in rural and underserved urban settings are largely unable or unwilling to participate in group exercise programs due in large part to their distance from such programs and financial considerations. Additionally, community based programs which provide social support and engagement have been shown to benefit elderly individuals as well as individuals with pathology, but are equally unattainable to this group. Taking the exercise to these individuals via telemedicine or tele-exercise may be an ideal means of delivering this type of intervention.

The long-term goal of this project is to improve outcomes for underserved populations of individuals with Parkinson disease (PD) by providing access to in-home physical activity via a telehealth approach. Approximately one million Americans currently live with a diagnosis of PD and it has been estimated that delaying the progression by 20% would result in a \$75,891 savings per individual based on reduced health care costs, income maintenance, increased duration of life and improved quality of life. However, individuals with PD of lower socioeconomic status, people of color and rural dwelling seniors have been critically underserved by clinical and academic programming resulting in poorer health outcomes.

These two studies will examine: 1) the Reach, Effectiveness, Implementation and Maintenance and 2) the optimal delivery method for an in-home exercise intervention program for individuals with PD living in underserved communities. We will deliver a managed and meaningful exercise intervention that not only addresses the benefits of physical activity for individuals with PD, but also offers a social connection to research staff outside of the participant's typical caregiver(s).

### **Study 1**

Examine the reach, effectiveness and maintenance of an in-home, partnered cycling program for underserved individuals with PD.

### **Study 2**

Examine the effects of social engagement during in-home exercise on a small sample of individuals with Parkinson Disease (PD). This pilot investigation will directly measure the effect of social support and engagement for rural dwelling individuals with PD.

## Background and Significance

It has been estimated that delaying the progression of PD by 20% would result in a life time savings of \$75,891 per individual based on lost income, health care costs, duration of life and quality of life (Johnson, Diener, Kaltenboeck, Birnbaum, & Siderowf, 2013). With approximately one million Americans currently living with a diagnosis of PD (de Lau & Breteler, 2006), the possible savings generated by quality interventions is remarkable. The currently accepted mechanisms for treatment of PD related symptoms include pharmacological, surgical and exercise related interventions; however, a large percentage of individuals have limited access to care (Dorsey & Willis, 2013). In many cases the limitations to receiving proper care are due to limited physical mobility, loss of driving ability, and distance from or access to a suitable healthcare provider (van der Marck et al., 2013). These limitations are particularly devastating for underserved individuals in lower socioeconomic status populations (SES) who may be fully unaware of current options for treatment and without access to programming that meets their needs. For example, individuals with PD in communities of color have far less access to and knowledge of activity-based intervention options.

In addition to postural instability, resting tremor, bradykinesia and rigidity (the four cardinal symptoms of PD), individuals with PD frequently report depression (Zesiewicz, Gold, Chari, & Hauser, 1999), cognitive impairment and dementia (Hely, Reid, Adena, Halliday, & Morris, 2008), and sleep disorders (Kumar, Bhatia, & Behari, 2002), among a host of other signs and symptoms. In the past ten years increasing evidence indicates that exercise, when well coupled with pharmacological approaches, may offer significant improvement in a number of areas affected by PD including: gait-related measures such as walking speed, stride length, balance and mobility (Alberts, Linder, Penko, Lowe, & Phillips, 2011; Earhart & Falvo, 2013; Hackney & Earhart, 2010; Herman, Giladi, & Hausdorff, 2009; Mehrholz et al., 2010), quality of life (Li et al., 2014; Nocera, Amano, Vallabhajosula, & Hass, 2013), depression (Boulgarides, Barakatt, & Coleman-Salgado, 2014; Sharma, Robbins, Wagner, & Colgrove, 2015) and sleep (Frazzitta et al., 2015; Wassom, Lyons, Pahwa, & Liu, 2015), just to name a few. Immediate improvements related to treadmill walking have been reported with only a single session (Frenkel-Toledo et al., 2005). Similarly, an anecdotal report of two days of tandem cycling reported symptom and handwriting improvements in a single individual with PD (Alberts et al., 2011). Numerous long term studies have shown improvements in gait-related measures with some research indicating that the benefits may be sustained for as long as five weeks after training (Herman, Giladi, Gruendlinger, & Hausdorff, 2007). What has not been explored well in the literature is the impact of these interventions on functional measures such as activities of daily living (ADLs). Additionally, while numerous effectiveness studies have been conducted on a myriad of interventions for individuals with PD, very few of these interventions have been progressed through a dissemination and implementation model to make them accessible and impactful to individuals living with PD and their care teams.

Focusing beyond the benefits of general exercise, a growing body of literature in both animal models (Poulton & Muir, 2005; Tillerson, Caudle, Reveron, & Miller, 2003) and humans (Alberts et al., 2011; Ridgel, Vitek, & Alberts, 2009) has demonstrated improvement of PD motor symptoms following “forced exercise” programs. In this context, forced exercise (FE) is defined as exercising at a rate greater than the individual’s preferred voluntary rate. Following eight weeks of either FE or voluntary rate exercise, individuals with PD who exercised in a FE group showed improvement in clinical ratings of their PD symptoms, biomechanical measures of dexterity and aerobic fitness. In contrast, individuals who exercised at their voluntary exertion level showed improvement in aerobic fitness only (Ridgel et al., 2009). An obvious challenge in the implementation of a FE model is how to progressively increase the intensity of the exercise while maintaining adherence.

Evidence indicates that group based exercise programs are more beneficial for a number of factors including program adherence and enjoyment (Shanahan et al., 2017; Zhou, Grady, & Chen, 2017). Although difficult to tease apart, the benefit of these social programs is thought to be in the person-to-person interactions that occur around the activity. This introduces a feasibility and scalability limitation to remotely delivered, in-home exercise interventions as it is not feasible to travel to the homes of more than a few individuals each day. One way to address this limitation is through person-to-person internet-based communication programs such as Skype© and FaceTime©. These tools allow the participants to communicate hands free while also allowing the clinician or researcher to visually monitor the participant. Face-to-face interactions with the participants allow for a member of the research team to monitor and provide feedback about exercise intensity. The social aspect of the experience is also enhanced when both parties can see each other. The difficulty in delivery of such an intervention is two-fold. First, how to use an internet-based communication tool with individuals who

may not have access to the necessary high-speed internet options; and second the scalability of one-on-one interactions with each participant. Additionally, it is unknown at this time if the face-to-face interaction is beneficial to the individual with PD.

Also missing from this literature is delivery of activity-focused interventions of any kind to individuals with PD in low SES communities. An unpublished zip code based demographic analysis of the 114 participants in a recently completed NIH R01 funded study on effective exercise approaches for individuals with PD found participants in the study resided in communities with only 31.3% of the households earned less than \$25,000 per year and 26.2% of the population earned more than \$100,000 per year. These percentages are vastly different than the 39.6% of the MO population that earns less than \$25,000 and 13.3% that earns over \$100,000. For individuals in lower SES communities, access to exercise programs is lacking.

The two studies described here seek to address the above highlighted problems in intervention implementation for individuals with PD in underserved communities. We will examine the effectiveness, feasibility, and ideal methodological approach for delivery of an in-home exercise program. This intervention will allow the individuals enrolled to participate in regular exercise and a community activity that promotes social support and engagement. Additionally, we will compare a solo versus partnered protocol to examine the possible benefits of partnered, socially supported exercise.

## Specific Aims

### **Study 1**

**SPECIFIC AIM 1:** Examine the reach and maintenance of an in-home cycling program for underserved individuals with PD. Reach will be assessed by examining the demographic characteristics of the individuals enrolled and through the administration of a questionnaire on objective and subjective socioeconomic status to better understand their level of accessibility to services, perceived barriers and economic status. We will also explore the implementation of a health coach to promote effective maintenance of the program after the 6-month intervention. Finally, we will conduct two interviews to better understand strengths and weakness of the program and to better address the needs of the participants in future studies.

**Hypothesis 1a:** Demographic characteristics including race and socioeconomic status of the enrolled participants will not statistically differ from the characteristics of the state of WI.

**Hypothesis 1b:** Feedback from participant interviews will inform future delivery of the in-home cycling program.

**SPECIFIC AIM 2:** Determine the effectiveness of a 6-month in-home, progressive, tele-exercise cycling program and 3-month health coach follow-up for underserved populations of individuals with PD.

**Hypothesis 2a:** Participants will improve performance of activities of daily living from baseline to posttest. These effects will be maintained at 3-month follow-up.

**Hypothesis 2b:** Participants will significantly improve measures of gait and balance performance and non-significantly improve fall rate from baseline to posttest. These effects will be maintained at 3-month follow-up in the group piloting implementation of a health coach, but not in solo follow-up group. Falls data will allow for effect size calculations for future applications.

**Hypothesis 2c:** Activity level as measured by an activity monitor will increase from baseline to posttest. This effect will be maintained at 3-month follow-up in health coach group, but not in the solo group.

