Study 2: 12 people with PD, living in rural settings or with barriers to travel and who have reported that proximity to community-based exercise is a primary barrier to enrollment will be enrolled in the study. Qualified individuals will be paired based on disease severity (score on subsection III of the UPDRS) and age and randomly assigned to either the social cycling group or solo cycling group for 6 months. Both groups will have an exercise bike delivered to their home, custom fit to their needs and installed in a safe location. Sessions will consist of up to 30 minutes of cycling. Those in the social group will cycling while engaged in social interaction with a research staff member, thus providing a social/community aspect that would not otherwise be present. Those in the solo group will have a target duration and intensity but will exercise without a partner.

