Flyers will only be posted after gaining permission at the site in question. To this end, we will contact other research colleagues at the University of Wisconsin, who are also working with elderly individuals and individuals with Parkinson disease (PD), including the Speech & Language Disorders Clinic of the Communication Sciences & Disorders Department and the UW Hospital Movement Disorders Clinic. Additionally, we will work with surrounding rural community hospitals asking them to post and handout the materials for their patients and patients' caregivers. We will also request permission through the UW Health Sports Medicine Fitness Center (UWHSMFC) in Madison, WI to disseminate the flyer to their Parkinson disease fitness classes, Falls Free Living class and similar programs targeted for elderly individuals and those with PD. We will also approach individuals at locations throughout the state where PD support classes and programming for elders is currently taking place. We will also work with the Wisconsin Chapter of the American Parkinson Disease Association, the Wisconsin Institute for Healthy Aging (WIHA), the Community Academic-Aging Research Network (CAARN), the Collaborative Center for Health Equity, and the Aging and Disability Research Centers (ADRC) of Milwaukee and Southwest WI to post notifications on their website and social networking accounts, as well as make presentations at local chapter support groups, events, and fundraisers. Finally, we will utilize the Sensory Motor Integration Laboratory's website and Facebook account to disseminate electronic information about the study.

**Privacy and Confidentiality:** One potential risk of participating in this study is that confidential information about the participants may be accidentally disclosed. If a participant's current diagnosis of PD is not known to others, the potential to cause damage to their psychological well-being as well as to their reputation exists.

To decrease this risk, data will be stored in a double secured location. In a locked filing cabinet (paper data) or on a secure network server.

All data collection sessions will occur in the private setting of the Sensory Motor Integration Lab. While multiple participants may be in the lab for data collections simultaneously, the lab is divided into three separate data collection areas which allows each participant to have maximum privacy.

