### **Baseline**

The baseline assessment is the same for both substudies.

All participants will complete approximately three hours of testing at each testing time point. All testing will occur in the on medication state. Testing will consist of biomechanical, non-motor features and disease severity data from each individual. The following are the specific assessment components for each time point:

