## Protocol in the Event of an Emergency During Data Collection Sessions in the UW – Natatorium

In the case of a medical emergency, a study team member will call 911, while a second team member stays with the participant. Standard lab operating procedure requires two individuals to be present in the lab during data collection sessions.

### Protocol in the Event of an Emergency During Monitored Cycling Sessions – Call 911

- a. Emergency preparedness – All research staff involved in the proposed intervention will be familiarized with the signs and symptoms of a medical emergency. As part of each participant's information folder, we will also have an emergency preparedness plan, which will include the following information:
  - The 10-digit telephone number to contact emergency services (the equivalent of 911) in the participant's local area
  - Special instructions to be given to emergency providers to access the individual in their home setting (i.e. gate codes or entrance locations).
  - Contact information for the participant's caregiver or emergency contact person
- b. Emergency response – The researcher will call 911 immediately if a participant presents with signs of a medical emergency or is unable to verbally respond. We will also call 911 if the participant falls and hits his/her head with or without loss of consciousness, or is unable to get up or move limbs. Once 911 has been contacted, the researcher will continue to monitor the situation via the bike's digital interface, while simultaneously contacting the participant's emergency contact. When emergency responders arrive, the researcher will provide any known details of the event, along with any requested information as noted in the preparedness plan. This information can be conveyed via the Skype connection or to the 911 operator during the call.

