## Power and Statistical Analysis

As this is a pilot study, we have not proposed a recruitment level that will properly power the outcome measures for a desired effect size. Previous work by [name] during her post-doctoral training under the guidance of [name] at Washington University in St. Louis indicate that approximately 27 individuals per group are needed to provide 89% power to detect differences in a similar intervention at a significance level of 0.05. This estimate uses gait velocity as the primary variable of interest and relies on a previous measured average forward gait velocity of  $1.2 \pm 0.1 \text{ m/s}$  and an average backward gait velocity of  $0.6 \pm 0.1 \text{ m/s}$  for 60 individuals with PD. The estimate is designed to detect a difference of 1 SD or  $0.1 \text{ m/s}$ , which is equivalent to an effect size of 0.4. Additionally, an attrition rate of approximately 15-20% should be expected. As the future RCT will likely focus on spatiotemporal measures collected during ADL task performance, this estimate provides some guidance for future work, but ideally future proposals will be powered from pilot data on the aims proposed herein. The proposed study of 40 individuals (20 per group) will provide pilot data which will be used to estimate effect size for the subsequent proposal (study 1).

To examine the reach of the project into the lower SES Parkinson disease community, we will analyze questions 6 and 7 of the MacArthur Scale of Subjective Social Status. A descriptive analysis of these data and subsequent comparison to income data for the state of WI will allow us to assess if individuals with PD in lower SES communities were optimally targeted.

To examine the qualitative effectiveness of the cycling intervention as well as the health coach intervention we will code the responses from the survey, assess common themes and use these data to inform the development of a larger RCT.

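### Study 1 measures reach only in people who attended a three-hour laboratory visit and plans no count of those who did not enrol, so the reach of the in-home programme cannot be estimated

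*Combined protocol and SAP*

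**What the plan says.** All places are in the combined protocol and SAP.

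- **Reach measure.** Specific Aims, Study 1, Aim 1: "Reach will be assessed by examining the demographic characteristics of the individuals enrolled". A questionnaire given to the same people adds their social and economic standing, how easily they can reach services, and the obstacles they see. Hypothesis 1a expects that race and "socioeconomic status of the enrolled participants will not statistically differ from the characteristics of the state of WI".
- **Reach analysis.** Power and Statistical Analysis takes questions 6 and 7 of the MacArthur scale and plans "A descriptive analysis of these data and subsequent comparison to income data for the state of WI". No participation rate, denominator or target is given.
- **Where and how long.** Privacy and Confidentiality: "All data collection sessions will occur in the private setting of the Sensory Motor Integration Lab". The emergency procedure is headed "Emergency During Data Collection Sessions in the UW – Natatorium". Baseline: "All participants will complete approximately three hours of testing at each testing time point".
- **What is collected there.** The Baseline assessment list includes the consent form, demographic data and the MacArthur scale. General Questionnaires adds that the demographic form is posted to the home, filled in there and brought to the visit.
- **What happens before.** Screening for eligibility describes a telephone screen for each interested person. Enrollment says that those who want to take part have their name and contact details entered in the participant database before the visit.

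**The concern.** The Project Summary says that distance and cost keep the target group out of existing exercise programmes, and home delivery is the answer to that. The Research Design section frames Study 1 with RE-AIM, in which reach is an explicit element. Yet a person enters the reach data only after a trip to the laboratory, and must come back for posttest and the 3-month follow-up. That makes three visits, or four for a Study 1 control, who also has a pre-test. No home assessment or travel support is described. The payment schedule compensates attendance but has no travel item.

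Someone who would gladly cycle at home but cannot or will not make the trip is therefore absent from every planned reach measure. Exclusion criterion 3 (unable to take part for the full duration) may also classify such a person as ineligible. The interviews on barriers (Improved Future Implementation) take place during the last cycling session, so only participants are asked.

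At stake is what the pilot can tell the larger trial. Low uptake could mean that home cycling is unattractive or that laboratory visits are, and these call for different designs.

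**Working it through.** The plan states no reach figure, so there is nothing to reproduce. The check traces who supplies reach data, then illustrates the consequence.

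**1. Path to the reach data.** Enquiry, phone screen, database entry and mailed packet, laboratory visit with consent and questionnaires, enrolment. Reach is computed at the last step. No section plans a count or description of people who leave at an earlier one.

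**2. Participation.** Input from the documents: 40 enrolled (Research Design). Assumed, because no counts are given: 60, 80 or 120 eligible enquirers. Participation is enrolled / eligible, with a Wilson 95% interval.

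- 40/60 = 67% (54 to 77)
- 40/80 = 50% (39 to 61)
- 40/120 = 33% (26 to 42)

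All three would give the same planned report.

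**3. Effect of travel on composition.** Let q be the share of distant people among eligible enquirers and r their chance of attending relative to the others (both assumed). Their share among those enrolled is qr / (qr + 1 − q). For q = 0.5 and r = 0.5 this is 0.25 / 0.75 = 33%.

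| q | r = 0.75 | r = 0.5 | r = 0.25 |
|---|---|---|---|
| 30% | 24% | 18% | 10% |
| 50% | 43% | 33% | 20% |
| 70% | 64% | 54% | 37% |

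So the visit lowers the observed share of distant people. This would show against the state figures only if distance goes with race or income, because distance and rurality are not themselves reach variables in Hypothesis 1a.

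**4. Why a favourable result would not settle it.** Hypothesis 1a treats the absence of a statistical difference as the expected outcome. No Wisconsin income figures are given, so as a stand-in take the Missouri figure in Background and Significance: 39.6% earning below $25,000. With n = 40 and an exact two-sided binomial test at 0.05 (assumed, as no test is named):

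- 9 of 40 gives p = 0.034 and 10 of 40 gives p = 0.074
- 22 of 40 gives p = 0.053 and 23 of 40 gives p = 0.024

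Any observed share from 10/40 = 25% to 22/40 = 55% is therefore non-significant. If the true share were 31.3%, as in the earlier exercise study that the same section describes as very unlike the state, power to detect it would be 15%.

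Step 3 can make reach look worse than home delivery alone would achieve. Steps 2 and 4 can let poor uptake or a skewed sample pass as adequate.

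**The case against.** A reader might infer that reach will be overstated. The documents do not support that. The stated measure is race and socioeconomic composition against the state. If the visit removes distant or poorer people, the sample moves away from that benchmark and reach looks worse. No participation rate is planned, so none can be inflated.

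A reader might also infer that people who decline leave no trace. That is too strong. Willing people have contact details on file before the visit and have been screened by telephone, so a ZIP code could probably be recovered for many of them. The protocol itself cites a ZIP-code analysis of earlier trial participants. What is missing is a plan to use such data, the reason for not enrolling, and any record of those who decline during the screening call.

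Three further points stand:

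- The wording about people "living in rural settings or with barriers to travel" describes Study 2, which has no reach aim, so the point is confined to Study 1. Study 1's target group also includes underserved urban residents, for whom distance may matter less.
- Some outcomes need laboratory equipment (the instrumented kitchen and the gait mat), and three or four paid visits are a lighter burden than regular classes. The point does not ask for the visits to change.
- Enquirers refer themselves, so even a complete screening log omits people who never made contact.

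None of this supplies the missing count or separates the two kinds of refusal.

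**Conclusion.** The point holds for Study 1 in limited form. Every planned reach measure comes from people who attended the laboratory visit, and no analysis covers screened people who did not enrol. Reach of the in-home programme cannot be estimated from this, and the direction of any misreporting is unknown.

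The size is also unknown, because the documents give no counts of enquirers, eligible people or travel refusals. The ranges of 33% to 67% participation and 10% to 64% distant people among those enrolled follow from assumed inputs and show sensitivity, not expected values. The 25% to 55% non-significant range rests on a Missouri benchmark and an assumed test. This is a pilot and the remedy is a cheap improvement. It should be made before recruitment, since reasons for refusal are hard to recover later.

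**What to change.** For Study 1:

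1. At the existing phone screen, record for every enquirer the ZIP code, race, household income, eligibility result and main reason for not enrolling, with travel to the laboratory as a listed option. Update the reason if a scheduled visit is later cancelled.
2. Count separately anyone excluded under criterion 3 because of travel.
3. In Specific Aim 1 and in Power and Statistical Analysis, report enrolled / eligible enquirers with a 95% confidence interval. Describe enrolled against non-enrolled people by ZIP-based rurality, race and income. Show travel refusals on their own line.
4. State that the denominator is self-referred enquirers, not all people with Parkinson disease in the state, and that subgroup rates will be imprecise with about 40 enrolled.

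Cost: a few minutes per screen, a small change to the verbal-consent script and some non-response on the income question. No added visits, participants or staff are needed.

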### **For both studies**

#### **Participants:**

Inclusion and exclusion criteria is identical for both studies.

Inclusion criteria for all enrolled participants include:

- 1) 45 years of age or older
- 2) diagnosis of idiopathic “definite PD” (Racette, Rundle, Parsian, & Perlmutter, 1999) based upon established criteria (Calne, Snow, & Lee, 1992; Hughes, Daniel, Kilford, & Lees, 1992)
- 3) vision at or corrected to 20/40 or better
- 4) ability to independently ambulate for at least 10 minutes continuously
- 5) no reported vestibular or neurological disease (stroke or muscle disease) beyond their diagnosed PD
- 6) score of greater than or equal to 78 (no evidence of dementia) on the telephone adaptation of the modified mini-mental state exam (Norton et al, 1999) .
- 7) English Speaking

Exclusion criteria for all enrolled participants include:

- 1) contraindication for exercise
- 2) history of muscular or orthopedic diagnosis

- 3) inability to participate in the full duration of the study.
- 4) currently exercising for 20 or more minutes per week.

**Participant Identification and Study Recruitment:** To recruit prospective participants to this study, we will utilize flyers, email, website and Facebook postings, presentations at support group meetings and special events, as well as word of mouth.

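### Study 1 judges reach against all Wisconsin residents although only people with PD aged 45 or older can enrol, so an age difference in income or race can be mistaken for good or poor reach

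*Combined protocol and SAP*

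**What the plan says.** Reach is half of Specific Aim 1 of Study 1: "Examine the reach and maintenance of an in-home cycling program for underserved individuals with PD". Its benchmark is given in two places.

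- Specific Aims, Study 1, Hypothesis 1a: "Demographic characteristics including race and socioeconomic status of the enrolled participants will not statistically differ from the characteristics of the state of WI".
- Power and Statistical Analysis: "we will analyze questions 6 and 7 of the MacArthur Scale of Subjective Social Status". The next sentence plans "A descriptive analysis of these data and subsequent comparison to income data for the state of WI", and uses the result to judge whether people with PD in lower-SES communities were well targeted.

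The Participants section sets the age floor at "45 years of age or older" and requires a definite diagnosis of idiopathic PD. No section restricts the state figures to that age range or to people with PD, standardises them for age, or names a source table. The analysis section calls the income analysis descriptive, names no test for it, and plans no comparison for race, although Hypothesis 1a includes race and speaks of a statistical difference.

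**The concern.** A reach comparison should show whether recruitment drew a fair share of the people it could have drawn. Here the two sides differ before recruitment starts, because residents under 45 count in the benchmark and cannot count in the sample. If income or racial mix varies with age in Wisconsin, that variation appears as a difference in reach.

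The error can run either way. If low income is more common at the enrolled ages than in the state as a whole, a programme with no special reach can look as if it reached poorer people. If it is less common, a fair sample can look as if it missed them. The same applies to race. A larger sample would not help, since it would only estimate the wrong contrast more precisely. The reach result is one of the products of this pilot, and a misread result could misdirect recruitment for the larger trial that is to follow.

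**Working it through.** The plan states no benchmark share, margin, power or test for reach, so there is no figure of its own to reproduce. The check asks how often a sample that perfectly mirrors its own age group would be called different from the state.

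**Inputs**

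- n = 40: Study 1 sample size (Research Design).
- Two-sided alpha = 0.05: an assumption. The plan states 0.05 only for the gait-velocity estimate.
- State share p0 = 0.20 for a characteristic such as low income or belonging to a racial minority: an assumption.
- True share p at the enrolled ages, from 0.08 to 0.35: an assumption that covers both directions.

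**Step 1. Rejection region.** Under p0 = 0.20 the expected count is 40 × 0.20 = 8. The exact two-sided binomial p-values at the edges are 0.048 for 3 of 40, 0.163 for 4, 0.072 for 13 and 0.027 for 14. The test therefore rejects at 3 or fewer, or at 14 or more.

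**Step 2. Probability of rejection.** With X ~ Binomial(40, p), this is P(X ≤ 3) + P(X ≥ 14).

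| True share at enrolled ages | Expected count | P(X ≤ 3) | P(X ≥ 14) | Called different |
|---|---|---|---|---|
| 8% | 3.2 | 0.601 | 0.000 | 0.601 |
| 10% | 4 | 0.423 | 0.000 | 0.423 |
| 15% | 6 | 0.130 | 0.001 | 0.132 |
| 20% (no age gap) | 8 | 0.029 | 0.019 | 0.048 |
| 25% | 10 | 0.005 | 0.103 | 0.108 |
| 30% | 12 | 0.001 | 0.297 | 0.297 |
| 35% | 14 | 0.000 | 0.559 | 0.559 |

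Every row describes a sample with no reach problem relative to its own age group. The excess over 0.048 comes from the reference alone.

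**Step 3. Other benchmarks.** For p0 from 0.10 to 0.396, the rejection rate is 3.0% to 4.8% with no age gap. It rises to 7% to 18% for a gap of +5 points and to 20% to 46% for +10 points.

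**Step 4. The descriptive reading.** If no test is done, the observed share is simply set beside the state share. The expected gap is then p − p0, for example 30% − 20% = 10 points, with no contribution from recruitment.

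**The case against.** The strongest reply is that this is a pilot that states openly that it is not powered. Reach is a single-sample, largely descriptive aim, and nothing in the randomised comparison, the safety plan or the sample size depends on it. A whole-state figure can also be a deliberate equity target: the investigators may want participants to look like Wisconsin, whatever the age mix of PD. Recruitment also runs through partners chosen for underserved groups, and reach is informed by questions on access and perceived barriers. All of this bears on severity, and it stands. It does not remove the mismatch, because the analysis section uses the state comparison to judge targeting.

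The rejection rates depend on carrying out Hypothesis 1a as a two-sided test at 0.05. The analysis section names no such test and no race comparison. That limit also stands, and without a test only the shift in Step 4 applies.

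Three stronger readings are tempting and are not supported.

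- A reader might infer a known direction: older people have lower incomes, so the programme will look better than it is. The documents hold no age-specific figures, and a floor of 45 also admits people of working age.
- A reader might count how often the sample merely exceeds the expected 8 of 40. The plan has no such success rule. Under Hypothesis 1a, moreover, a significant difference in either direction contradicts the hypothesis.
- A reader might see the same age mismatch in Background and Significance, where "participants in the study resided in communities with only 31.3% of the households earned less than" a stated income is called "vastly different than the 39.6% of the MO population". That passage sets figures for participants' zip-code communities against a state figure, with no age limit stated on either side. The ages of the participants do not enter directly, so it does not share this problem.

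**Conclusion.** The mismatch is in the text and nothing elsewhere corrects it: an all-age, all-health benchmark is set against a sample restricted to age 45 or older with PD. An age difference in income or race can therefore be mistaken for good or poor reach. That it will be, or in which direction, cannot be shown from the documents.

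The size is conditional. With a 20% benchmark, 40 participants and a two-sided 0.05 test, a gap of 5 points in either direction gives a false difference in 11% to 13% of trials, against about 5% with a matched reference. Gaps of 10 and 15 points upward give 30% and 56%; gaps of 10 and 12 points downward give 42% and 60%. If the Wisconsin shares at the enrolled ages are close to the all-age shares, the effect is negligible.

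The point is minor. It affects the interpretation of one pilot aim and leaves the randomised comparison untouched.

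**What to change.** In Hypothesis 1a and in Power and Statistical Analysis, replace the state of Wisconsin as comparator with Wisconsin residents aged 45 or older, standardised to the age distribution of the enrolled sample. Name the source table. Compare income in the same unit, household or personal, as the questionnaire item used. Keep the all-age state figure as a secondary, descriptive equity reference. Add one sentence stating that the age-matched reference is still not specific to people with PD, so any PD-related difference in income or race remains in the comparison.

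The cost is wording in two places, reliance on public tables by age, and slightly more analysis work. It needs no new data and no additional participants.
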